4.1 Primary Endpoints and Assessment Methods

See Section 9.1 of the protocol.

4.2 Secondary Endpoints and Assessment Methods

See Section 9.2 of the protocol.

AOM, ALRI, and hospitalization recorded in the CRB as associated to an ILI and occurring within 30 days after the ILI onset of any will be considered as associated with the ILI.

4.3 Observational Endpoints and Assessment Methods

See Section 9.3 of the protocol.

4.4 Derived Endpoints: Calculation Methods

4.4.1 Safety

4.4.1.1 Solicited Reactions

4.4.1.1.1 Daily Intensity

All daily records for solicited reactions will be derived into daily intensity according to the following classification: None, Grade 1, Grade 2, Grade 3, or Missing.

For the derivation of daily intensities, the following sequential steps will be applied:

- Solicited reactions (except Fever / Pyrexia) with an investigator presence recorded as “No” and with all daily records missing then all daily intensities will be derived as None.
- For non-measurable solicited reactions, daily intensities will correspond to daily records reported in the clinical database. For measurable solicited reactions the daily measurements reported in the clinical database will be converted based upon the intensity scales defined in the protocol; this assumes a reaction that is too large to measure (non-measurable, “NM”) is Grade 3.

Note: The maximum intensity on the ongoing period is derived from the record of the maximum intensity / measurement after the end of the solicited period following the rule described above.

Solicited reactions (except Fever / Pyrexia) with an investigator presence recorded as “No” and with all daily records missing then all daily intensities will be derived as None.

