13.2 Source Data and Source Documents

“Source data” are the data contained in source documents. Source documents are original documents or certified copies, and include, but are not limited to, diary cards, medical and hospital records, screening logs, informed consent / assent forms, telephone contact logs, and worksheets. The purpose of study source documents is to document the existence of subjects and to substantiate the integrity of the study data collected. Investigators must maintain source documents so that they are accurate, complete, legible, and up to date.

For missing or discrepant data on a diary card, the study coordinator will obtain verbal clarification from the subject, enter the response into the “investigator’s comment” page of the diary card, and transfer the information to the CRB.

The subject pre-screening log should list all individuals contacted by the Investigators to participate in the study, regardless of the outcome.

The Investigator must print^a any electronic records on an ongoing basis, sign and date them immediately after creation, and keep the printouts on file as source documents that can be verified by the Sponsor or an inspector against the electronic records. Any subsequent changes of an electronic record require the record to be re-printed, dated (with an indication of the date of change), and signed. Such records must also be kept together with the original printed copy.

Good Documentation Practice should be followed by the Investigator and the site staff managing source documents.

^a Unless the electronic medical records are managed by validated computerized systems that are compliant with US 21 CFR Part 11, in which case they are acceptable on their own.

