4.4.1.1.2 Maximum Overall Intensity

Maximum overall intensity will be derived from the daily intensities computed as described in [Section 4.4.1.1.1](#) and is calculated as the maximum of the daily intensities over the period considered.

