4.4.1.1.3 Presence

Presence will be derived from the maximum overall intensity on the period considered:

- None: No presence
- Grade 1, Grade 2, or Grade 3: Presence
- Missing: Missing presence

Subjects with at least one non-missing presence for a specific endpoint will be included in the analysis. Conversely, those without a non-missing presence will not be included in the analysis of the endpoint.

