5.3.3.4 Intensity

For solicited reactions, missing intensities will be handled as described in [Section 4.4.1.1.1](#). For unsolicited AEs, missing intensities will remain missing and will not be imputed.

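### For non-fever solicited reactions, the SAP uses an investigator No when daily records are absent but has no rule for a Yes, so any such child drops out and rates can only move down

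*SAP*

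**What the plan says.** SAP 4.4.1.1.1 derives daily intensity in sequential steps. Where the investigator answered No, the first step reads "and with all daily records missing then all daily intensities will be derived as None". Its scope, set at the start of that same sentence, leaves out fever and depends on the investigator's answer: "Solicited reactions (except Fever / Pyrexia) with an investigator presence recorded as". The later step works only from daily data: "For non-measurable solicited reactions, daily intensities will correspond to daily records reported in the clinical database", and for measurable reactions the daily measurements are converted to grades. No step covers an investigator Yes with every daily record missing.

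SAP 4.4.1.1.2 then defines the maximum overall intensity, which "is calculated as the maximum of the daily intensities over the period considered". SAP 4.4.1.1.3 derives presence from that maximum, with the line "Missing: Missing presence", and adds that "those without a non-missing presence will not be included in the analysis of the endpoint".

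The missing-data section supplies nothing further. SAP 5.3.3.4 only points back: "For solicited reactions, missing intensities will be handled as described in" 4.4.1.1.1. Protocol 12.3.3 says missing safety data are not replaced. For summaries after any dose, SAP 4.4.1.4.2 takes the worst case over injections.

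**The concern.** The same field, completed by the same investigator, is used when it is negative and ignored when it is positive. A recorded negative without daily detail keeps the child in the denominator. A recorded positive without daily detail removes the child from both numerator and denominator. Where this happens, the error has a fixed direction: the vaccine looks better tolerated.

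Solicited reactions are a secondary safety endpoint (Protocol 9.3.3.1) in children 6 through 35 months of age. Protocol 1.2 already reports slightly more injection-site reactogenicity with QIV-HD than with QIV-SD in Phase II. The SAP's other main safety default is conservative: in 5.3.3.2 a missing relationship to vaccine counts as related. This derivation runs the other way.

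The situation can be foreseen. A parent may remember that a reaction occurred without being able to give day-by-day grades or sizes. The SAP itself expects investigator answers without daily records, because it provides a rule for the No half.

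**Working it through.** The plan states no figure on this point, so there is none to reproduce. The check follows one child through the text and then does the algebra.

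**Scope.** Protocol Tables 9.2 and 9.3 list 5 injection-site and 6 systemic reactions. Without fever, 10 of the 11 are affected.

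**Path of a child with all daily records missing, one dose**

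| Step | Investigator No | Investigator Yes |
|---|---|---|
| Daily intensity (4.4.1.1.1) | None on every day | no rule, so Missing |
| Maximum intensity (4.4.1.1.2) | None | Missing |
| Presence (4.4.1.1.3) | No presence | Missing presence |
| In the analysis? | yes, as a non-reactor | no |

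The right-hand column follows from the general rules; the SAP does not name this case.

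**Size, one dose.** Let p be the true share of children with the reaction, taking the investigator answer as correct, and y the share of Yes children with no daily record at all. Children answered No contribute fully whether or not they have records, so their missingness does not enter. Per N children:

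- numerator = N·p(1−y)
- denominator = N(1−p) + N·p(1−y) = N(1−py)
- reported rate = p(1−y)/(1−py)
- shortfall = p − p(1−y)/(1−py) = p·y(1−p)/(1−py), which is never negative

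Example: p = 0.40, y = 0.05 gives 0.38/0.98 = 38.78%, a shortfall of 1.22 points.

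| True p (assumed) | y = 2% | y = 5% | y = 10% |
|---|---|---|---|
| 5% | 4.90% | 4.76% | 4.52% |
| 20% | 19.68% | 19.19% | 18.37% |
| 40% | 39.52% | 38.78% | 37.50% |

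At y = 0 the shortfall is zero.

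**Between-arm difference.** Take 40% against 30% with the same y in both arms:

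- y = 2%: 39.52 − 29.58 = 9.94 points
- y = 5%: 38.78 − 28.93 = 9.84 points (rounded from unrounded rates)
- y = 10%: 9.66 points

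**After any dose.** A two-dose child with a Yes and no records after one dose, and None after the other, has one non-missing presence. Under 4.4.1.1.3 and 4.4.1.4.2 that child could be tabulated as a non-reactor. If every affected child were of this kind, and y is now the share of any-dose reactors so affected, the rate would be p(1−y). For p = 40% and y = 5% that is 38.0%, slightly further down than the per-dose figure.

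**Fever.** The investigator answer is not used in either direction, so both kinds of child are dropped and this asymmetry does not arise.

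**The case against.** The strongest reply is that the two cases are not mirror images. A No with blank days is a recorded negative, and coding it None is sensible. A Yes with every day blank is an incomplete record, and the plan provides for resolving such records. Protocol 11.1 has the investigator clarify incomplete diary entries and explain all missing information. Protocol 11.2 applies consistency checks and queries, and 13.4.1 requires data queries to be completed before lock. Protocol 13.2 adds: "For missing or discrepant data on a diary card, the study coordinator will obtain verbal clarification from the subject". One graded day is enough to keep a child. This stands as an argument that few cases will remain. It does not supply a rule for those that do, and verbal clarification may produce exactly a Yes without daily grades.

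A second reply is that such children are not established reactors. A solicited reaction needs onset in Day 0 to Day 7 (Protocol 9.3.3.2), and measurable reactions are graded from sizes at analysis. That is fair: the grade is unknown and the onset day unconfirmed. It supports showing them as grade missing, not dropping them while the matching No is accepted without records.

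A reader might also infer that both answers without records should be treated as missing, as for fever. That would discard recorded negatives. With p = 40%, records for all Yes children and blank days for half of the No children, the rate would be 0.40/(0.40 + 0.30) = 57%, a far larger error in the other direction. Fever is a weak precedent, because temperature is recorded daily whether or not there is a reaction.

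**Conclusion.** The point holds for the 10 non-fever solicited reactions as a gap in the derivation. Its effect is conditional. If any Yes child still has no daily records after queries, that child is dropped for the dose, or may count as a non-reactor after any dose, and the reported rate can only fall.

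A reader might infer that the reported rates are in fact biased downward by a material amount. The documents do not support that: they give neither p nor y, the effect vanishes at y = 0, and the query steps should keep y small. Nor may y be read as the overall share of children without daily records, because blank days under No do no harm.

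Over the assumed values above, the shortfall runs from about 0.1 point (p = 5%, y = 2%) to 2.5 points (p = 40%, y = 10%). A 10-point between-arm difference shrinks to between 9.94 and 9.66 points. That last result rests on a similar y in both arms, which the blinding of parents and safety assessors makes plausible but does not guarantee. Safety is described without hypothesis tests (SAP 5.1.2.2), so no confirmatory conclusion is affected. It is a small correction, worth making before unblinding because the error has only one possible direction.

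**What to change.** Add to SAP 4.4.1.1.1 and 4.4.1.1.3, for non-fever solicited reactions, that an investigator Yes with all daily records missing gives presence = Yes with intensity missing. Count such children in the numerator and denominator of the row for any reaction, and show them in a separate grade-missing row. State in 4.4.1.4.2 that the same handling applies after any dose, so that None after the other dose cannot override a Yes. Report the number of such children by arm. Keep the existing rule that No with all daily records missing is None.

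The cost is one line of derivation, one table row and a count. The field is already collected. The downside for the sponsor is that reported rates become slightly less favourable if such children exist.

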4.4.1.1.2 Maximum Overall Intensity

Maximum overall intensity will be derived from the daily intensities computed as described in [Section 4.4.1.1.1](#) and is calculated as the maximum of the daily intensities over the period considered.

4.4.1.1.3 Presence

Presence will be derived from the maximum overall intensity on the period considered:

- None: No presence
- Grade 1, Grade 2, or Grade 3: Presence
- Missing: Missing presence

Subjects with at least one non-missing presence for a specific endpoint will be included in the analysis. Conversely, those without a non-missing presence will not be included in the analysis of the endpoint.

4.4.1.1.4 Time Period

Time period when at least one daily intensity Grade 1, Grade 2 or Grade 3 of a solicited reaction is present will be categorized and displayed as D0-D3, D4-D7, D8 or later.

4.4.1.1.5 Time of Onset

Time of onset will be derived from the daily intensities computed as described in [Section 4.4.1.1.1](#). It corresponds to the first day with intensity of Grade 1, Grade 2, or Grade 3.

Time of onset will be categorized into and displayed as D0-D3 and D4-D7.

Note: If a reaction was not continuous (ie, reaction occurs over 2 separate periods of time intervened by at least one daily intensity Missing or None) then the time of onset was the first day of the first occurrence.

4.4.1.1.6 Number of Days of Occurrence

Number of days of occurrence over the period considered will be derived from the daily intensities computed as described in [Section 4.4.1.1.1](#). It corresponds to the number of days with daily intensities of Grade 1, Grade 2, or Grade 3.

Number of days of occurrence will be categorized into and displayed as 1-3 days, 4-7 days, and 8 days.

4.4.1.1.7 Ongoing

Ongoing will be derived from the last daily intensity of the solicited period computed as described in [Section 4.4.1.1.1](#) and the maximum intensity on the ongoing period. The investigator's ongoing flag is not used because the measurement would determine the ongoing status of the reaction.

If the last daily intensity of the solicited period was at least Grade 1 and maximum intensity on the ongoing period is also at least Grade 1, then the reaction is considered ongoing. In any other cases the reaction is not be considered as ongoing.

4.4.1.2 Unsolicited Non-serious AEs

4.4.1.2.1 Presence

An observation will be considered an event if it has at least a verbatim term and is not a Grade 0 intensity event. Grade 0 events should be included in the listing "Unsolicited non-serious adverse events not included in the safety analysis" and Grade 0 events with "Serious" checked should be included in the listing "Unsolicited serious adverse events not included in the safety analysis".

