- To compare the HAI immune response of QIV-HD to QIV-SD in subjects 6 months through 35 months of age
- To describe the HAI immune response induced by each vaccine against the 4 vaccine strains and according to the different strain formulations used in each of the study influenza seasons
- To describe the SN immune response induced by QIV-HD or QIV-SD against the 4 QIV-HD vaccine strains in a randomized subset of subjects
- To describe the anti-neuraminidase (NA) immune response induced by QIV-HD or QIV-SD in a randomized subset of subjects

Re-vaccination Response

To describe the immune response (HAI method) to vaccination in Season 3 (NH) among subjects re-enrolled from Season 1 (NH) to Season 3 (NH), according to the vaccines received in both Season 1 (NH) and Season 3 (NH)

Safety

- To describe the safety profile (injection site reactions and systemic events) of each vaccine during the 28 days following each vaccination for the ESafAS (all subjects from Sentinel Safety Cohort, all subjects from Season 1, and a subset of subjects from Seasons 2 and 3)
- To describe all SAEs (including AESIs) up to at least 180 days after the last vaccination in all subjects

The endpoints for the secondary objectives are presented in [Section 9.3](#)

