9.3.3 Safety

9.3.3.1 Safety Endpoints

Reactogenicity will be described for the ESafAS:

- Occurrence of any unsolicited systemic AEs reported in the 30 minutes after each vaccination
- Occurrence of solicited (pre-listed in the subject's diary card and CRB) injection site reactions and systemic reactions occurring up to 7 days after vaccination
- Occurrence of unsolicited AEs up to 28 days after vaccination

SAEs/AESIs will be described in all subjects:

- Occurrence of SAEs (including AESIs) throughout the study
- Occurrence of AESIs throughout the study

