9.3.3.2 Safety Definitions

The following definitions are taken from the ICH E2A Guideline for Clinical Safety Data Management: Definitions and Standards for Expedited Reporting.

Adverse Event (AE):

An AE is any untoward medical occurrence in a patient or in a clinical investigation subject administered a medicinal product and which does not necessarily have a causal relationship with this treatment. An AE can therefore be any unfavorable and unintended sign (including an abnormal laboratory finding, for example), symptom or disease temporally associated with the use of a medicinal product, whether or not considered related to the medicinal product.

Therefore an AE may be:

- A new illness
- The worsening of a pre-existing condition
- An effect of the vaccination, including the comparator
- A combination of the above

All AEs include serious and non-serious AEs.

Surgical procedures are not AEs; they are the actions taken to treat a medical condition. It is the condition leading to the action taken that is the AE (if it occurs during the study period).

Pre-existing medical conditions are not to be reported as AEs. However, if a pre-existing medical condition worsens following study interventions in frequency or intensity, or if according to the Investigator there is a change in its clinical significance, this change should be reported as an AE (exacerbation). This applies equally to recurring episodes of pre-existing conditions (eg, asthma) if the frequency or intensity increases post-vaccination.

Serious Adverse Event (SAE):

Serious and *severe* are not synonymous. The term *severe* is often used to describe the intensity of a specific event as corresponding to Grade 3. This is not the same as *serious*, which is based on subject / event outcome or action criteria usually associated with events that pose a threat to a subject's life or functioning. Seriousness, not severity, serves as a guide for defining regulatory reporting obligations.

An SAE is any untoward medical occurrence that at any dose

- Results in death

- Is life-threatening^a
Requires inpatient hospitalization or prolongation of existing hospitalization^b
- Results in persistent or significant disability / incapacity^c
- Is a congenital anomaly / birth defect
- Is an important medical event (IME)

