Definition	Pain when the injection site is touched or injected limb mobilized	Presence of a redness including the approximate point of needle entry	Swelling at or near the injection site Swelling or edema is caused by a fluid infiltration in tissue or cavity and, depending on the space available for the fluid to disperse, swelling may be either soft (typically) or firm (less typical) to touch and thus can be best described by looking at the size of the swelling	Hardening at or near the injection site. Hardening is caused by a slow diffusion of the product in the tissue leading to a thick or hard area to touch at or near the injection site and thus can be best described by looking at the size of the hardening.	Bruising is the result of the diffusion of blood in the skin from ruptured blood vessels that forms a purple or black and blue spot on the skin. It can be best described by looking at its size.

CRB term (MedDRA LLT)	Injection site tenderness	Injection site erythema	Injection site swelling	Injection site induration	Injection site bruising
Intensity scale*	
Grade 1: Minor reaction when injection site is touched
 
Grade 2: Cries or protests when injection site is touched
 
Grade 3 (CRB): Cries when injected limb is mobilized, or the movement of the injected limb is reduced
 
Grade 3 (diary card): Cries when injected limb is moved or the movement of the injected limb is reduced
	
Grade 1: > 0 to < 25 mm
 
Grade 2: ≥ 25 to < 50 mm
 
Grade 3: ≥ 50 mm
	
Grade 1: > 0 to < 25 mm
 
Grade 2: ≥ 25 to < 50 mm
 
Grade 3: ≥ 50 mm
	
Grade 1: > 0 to < 25 mm
 
Grade 2: ≥ 25 to < 50 mm
 
Grade 3: ≥ 50 mm
	
Grade 1: > 0 to < 25 mm
 
Grade 2: ≥ 25 to < 50 mm
 
Grade 3: ≥ 50 mm

* For the subjective reaction of tenderness, parents /guardians will record the intensity level (Grade 1, 2, or 3) in the diary card. For the measurable reactions of redness and swelling, they will record just the size of the reaction, and the classification as Grade 1, 2, or 3 will be assigned at the time of the statistical analysis.

Table 9.3: Solicited systemic reactions for children 6 through 35 months of age: terminology, definitions, and intensity scales

CRB term (MedDRA LLT)	Fever	Vomiting	Crying abnormal	Drowsiness	Appetite lost	Irritability
MedDRA PT	Pyrexia	Vomiting	Crying	Somnolence	Decreased appetite	Irritability

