Diary card term	Temperature	Vomiting	Abnormal crying	Drowsiness	Loss of appetite	Irritability
Definition	Elevation of temperature to $\geq 38.0^{\circ}\text{C}$ ($\geq 100.4^{\circ}\text{F}$)	Vomiting does not include spitting up	Inconsolable crying without a determined reason	Reduced interest in surroundings, or increased sleeping	See intensity scale	An excessive response to stimuli: increased fussiness, whining, and fretfulness despite attempts to comfort the infant and despite caregiver responses that would normally be soothing
Intensity scale*	Grade 1: $\geq 38.0^{\circ}\text{C}$ to $\leq 38.5^{\circ}\text{C}$ or $\geq 100.4^{\circ}\text{F}$ to $\leq 101.3^{\circ}\text{F}$ Grade 2: $> 38.5^{\circ}\text{C}$ to $\leq 39.5^{\circ}\text{C}$ or $> 101.3^{\circ}\text{F}$ to $\leq 103.1^{\circ}\text{F}$ Grade 3: $> 39.5^{\circ}\text{C}$ or $> 103.1^{\circ}\text{F}$	Grade 1: 1 episode per 24 hours Grade 2: 2–5 episodes per 24 hours Grade 3: ≥ 6 episodes per 24 hours or requiring parenteral hydration	Grade 1: < 1 hour Grade 2: 1–3 hours Grade 3: > 3 hours	Grade 1: Sleepier than usual or less interested in surroundings Grade 2: Not interested in surroundings or did not wake up for a feed / meal Grade 3: Sleeping most of the time or difficult to wake up	Grade 1: Eating less than normal Grade 2: Missed 1 or 2 feeds / meals completely Grade 3: Refuses ≥ 3 feeds / meals or refuses most feeds / meals	Grade 1: Easily consolable Grade 2: Requiring increased attention Grade 3: Inconsolable

* For all reactions but fever, parents / guardians will record the intensity level (Grade 1, 2, or 3) in the diary card. For fever, they will record the body temperature, and the classification as Grade 1, 2, or 3 will be assigned at the time of the statistical analysis based on the unit used to measure the temperature and the intensity scale.

Important notes for the accurate assessment of temperature:

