4.4.1.3 SAEs

AESIs will be collected from inclusion until the end of the study as SAEs. AESIs are to be reported and analyzed as SAEs.

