4.4.1.3.2 Time of Onset

Time of onset will be computed using the same methodology as for unsolicited non-serious AEs described in [Section 4.4.1.2.4](#).

SAEs will be analyzed throughout the study using the following periods:

- Within 28 days after each and any injection
- Within 180 days from 28 days after the last injection
- During the study (ie, all SAEs occurred during the study)

An SAE with missing time of onset will be considered to have occurred just after the vaccination, indicated by the visit number, and will be included in these tables.

Note: SAEs that occurred before the 1st vaccination (ie, negative time of onset or with a time of onset higher than defined 28 days) will not be included in analysis but may be listed separately.

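### The SAP lists but does not count Grade 0 events marked serious, although the protocol's objective and endpoint cover all SAEs; the reach is very narrow

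*SAP*

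**What the plan says.** SAP 4.4.1.2.1 (Presence) falls within 4.4.1.2, the section on unsolicited non-serious AEs. It accepts an observation as an event only if it has a verbatim term and is not Grade 0. It then goes beyond its heading: Grade 0 records with Serious ticked go to a listing called "Unsolicited serious adverse events not included in the safety analysis".

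The protocol's safety objective (2.2) is "To describe all SAEs (including AESIs) up to at least 180 days after the last vaccination in all subjects". The matching endpoint (9.3.3.1) is "Occurrence of SAEs (including AESIs) throughout the study". Protocol 9.3.3.2 separates seriousness from severity and describes the former as something "which is based on subject / event outcome or action criteria".

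SAP 4.4.1.3 deals with SAEs and adds that "AESIs are to be reported and analyzed as SAEs". Its time-of-onset subsection (4.4.1.3.2) gives as its third analysis period "During the study (ie, all SAEs occurred during the study"). The only exclusion stated there is by onset time. SAP 5.7 declares no change to the planned analyses.

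**The concern.** A record that the investigator has marked serious is an SAE under the protocol whatever its grade. The SAP uses the grade to take such a record out of the SAE tables and leaves it only in a listing whose title places it outside the safety analysis. If one is still in the database at lock, the tables show fewer SAEs than investigators declared. AESIs follow the SAE path, so they would be dropped in the same way.

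The placement is a second problem. A rule about serious events under a non-serious heading, with no presence rule in the SAE section, leaves a programmer to guess whether it applies to the SAE tables.

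**Working it through.** The documents give no figure for this point, so there is none to reproduce. The check compares the texts, then asks how a Grade 0 serious record could arise, then gives a sense of scale.

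**1. Is there a conflict?**

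| Source | Condition for an SAE to count |
|---|---|
| Protocol 9.3.3.2 | Outcome or action criteria; no grade |
| Protocol 2.2 and 9.3.3.1 | All SAEs, throughout the study; no grade |
| SAP 4.4.1.3.2 | All SAEs in the study period; exclusion by onset time only |
| SAP 4.4.1.2.1 | Must not be Grade 0, even when Serious is ticked |

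The last row adds a condition that the others lack, and SAP 4.4.1.3 to 4.4.1.3.2 do not lift it. The SAP 4.4.1.3.2 row is the weakest support, because its wording mainly defines a time window. The conflict stands on the protocol rows alone.

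**2. How could a Grade 0 serious record arise?**

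- *Recorded directly.* Protocol 9.3.3.3.3 grades unsolicited AEs, serious or not, on a scale of 1 to 3, so a recorded 0 is off-scale. A missing intensity stays missing (SAP 5.3.3.4) and is not Grade 0.
- *Derived from a measurement.* Protocol 9.3.3.3.3 grades measurable AEs on the solicited list by the solicited scales. Table 9.2 has 5 injection-site terms and Table 9.3 has 6 systemic terms: 5 + 6 = 11. Those graded by measurement are 4 in mm (erythema, swelling, induration, bruising) and 1 by temperature (fever): 4 + 1 = 5.
  - For the 4 sized terms the scale starts at "Grade 1: > 0 to < 25 mm", so any positive size is at least Grade 1: 0 of 4 can fall below it.
  - For fever the grade is assigned from the temperature ("For fever, they will record the body temperature"), and Grade 1 starts at 38.0 °C, so a lower reading gets no grade: 1 of 1.
  - Result: 1 of 11 terms. Even this needs a derived intensity of None (the category in SAP 4.4.1.2.2) to be treated as Grade 0, which the SAP does not say.
- *AESIs.* None of the 6 AESI categories is graded by measurement: 0 of 6. They are reachable only through a data-entry anomaly.

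**3. Scale, for illustration only**

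SAP 5.5 plans 13,220 randomized subjects at 1:1, so 13,220 / 2 = 6,610 per arm. The number of affected subjects k in one arm is an assumption; the range 0 to 3 is shown. Each affected subject is taken to have no other SAE. Intervals are exact (Clopper-Pearson), the SAP's method for a single proportion.

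| k | k / 6,610 | 95% CI |
|---|---|---|
| 0 | 0% | 0 to 0.056% |
| 1 | 0.015% | 0.0004 to 0.084% |
| 2 | 0.030% | 0.004 to 0.109% |
| 3 | 0.045% | 0.009 to 0.133% |

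If the 100 sentinel subjects are pooled into QIV-HD (6,610 + 100 = 6,710), one subject is again 0.015% (0.0004 to 0.083%). A subject with another counted SAE changes the event count but not the subject percentage.

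**The case against.** The strongest reply is that the rule defines what an event is and removes no genuine SAE. Under the protocol an SAE must first be an untoward medical occurrence, and a ticked box does not supply one. Since no valid grade is 0, a Grade 0 record is invalid, and a temperature below 38.0 °C is not fever by the protocol's own definition. On this view every real SAE is still counted.

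The safeguards are also substantial. Protocol 11.2 provides for consistency checks and queries, and it releases the database only after SAE data have been reconciled with pharmacovigilance. SAP 5.6 plans a blind review before lock. Finally, the objective is descriptive and a listing does disclose the records, while counting every ticked record risks counting a mis-tick.

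Much of this stands as to size: such records should be very rare, they remain visible, and the wording in SAP 4.4.1.3.2 should not carry much weight. It does not rescue the rule. The protocol makes no exception for a low or off-scale grade when the investigator has declared an event serious. If the tick is wrong, a query should correct it; an analysis rule should not override it. The checks may reduce the number of such records, but they do not change what happens to any that remain. By naming a listing for them, the SAP allows for some reaching analysis.

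**Conclusion.** The concern holds. SAP 4.4.1.2.1 excludes from the SAE counts a class of records that the protocol's objective, endpoint and definition include. The direction is fixed: each such record lowers the SAE event count by one, and none can raise it.

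The size is very small and may be zero; the documents give no expected number of these records. The effect is confined to the descriptive SAE tables. Hypothesis tests, alpha, expedited reporting and pharmacovigilance reconciliation are unaffected. This is a minor correction worth making because the stated rule is wrong, with no suggestion that the safety conclusions are at risk. The conclusion assumes that a ticked Serious box left unchanged at lock represents the investigator's judgment.

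**What to change.** 1. In SAP 4.4.1.2.1, limit the Grade 0 exclusion to non-serious events and drop the listing of excluded serious events.
2. Query every Grade 0 record marked serious before database lock, so that either the grade or the Serious box is corrected.
3. In SAP 4.4.1.3, state that any event still marked serious at lock, AESIs included, is counted in the SAE analysis whatever its recorded or derived intensity, with intensity shown as reported or as missing.

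The cost is two or three SAP sentences and one query rule within the checks that Protocol 11.2 already plans. The one downside is that a box ticked in error and not corrected by query would be counted as an SAE.
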